#### **5.1.4.2 Management of Rucaparib Treatment-Emergent Creatinine Elevations**

Rucaparib is a potent inhibitor of MATE1 and MATE2-K transporters, which are involved in active secretion of creatinine. Rucaparib-mediated creatinine elevation occurs early in treatment and then stabilizes. Creatinine elevation is not typically accompanied by elevations in urea (BUN). Creatinine elevation resolves with *treatment interruption* of rucaparib and recurs with re-challenge. Creatinine elevation has not been associated with evidence or reports of permanent renal impairment. The following are guidelines for rucaparib dose modifications in the events of Grade  $\geq 3$  creatinine elevations:

- For Grade 4 isolated creatinine elevations (BUN  $\leq$  ULN), hold rucaparib and investigate with ultrasound, urinalysis, and so on for potential alternative etiologies. When other reversible causes are treated or ruled out and the event has resolved to Grade 1 or better, then resume rucaparib at a reduced dose.
- For Grade 3 isolated creatinine elevations (BUN  $\leq$  ULN), investigate with ultrasound, urinalysis, and so on for potential alternative etiologies. In the absence of another reversible cause (e.g., obstructions or infections) or evidence of renal injury, continue rucaparib at the same dose. Hold rucaparib for other reversible causes until the patient is treated and the event has resolved to Grade 1 or better, and then resume rucaparib at the same dose.

#### **5.1.4.3 Management of Treatment-Emergent Diarrhea**

Diarrhea has been associated with both ipatasertib and rucaparib administration.

For diarrhea occurring after Cycle 2 that persists for more than 5 days, despite treatment with an anti-diarrheal agent, a stool culture for infectious workup (i.e., *Clostridium difficile*, enteric bacteria, cytomegalovirus) will be obtained, and diarrhea should be treated with the appropriate antibiotic.

**Table 5 Diarrhea Management Guidelines**

Severity of Diarrhea	Management Guideline
Grade 1	
Continue study drugs at the current dose level.
 
Manage with loperamide 4 mg initially, and then 2 mg every 4 hours or after every unformed stool until after 12-hour diarrhea-free interval.
 
Dietary modifications such as avoiding any lactose-containing foods.
 
Hydration with 8–10 glasses of clear liquid such as broth and low-calorie electrolyte-enhanced drinks per day.

Grade 2	
Manage with loperamide as early as possible 4 mg initially, and then 2 mg every 4 hours or after every unformed stool until after 12-hour diarrhea-free interval.
 
Dietary modifications such as avoiding any lactose-containing foods.
 
Hydration with 8–10 glasses of clear liquid, such as broth and low-calorie electrolyte-enhanced drinks, per day.
 
For non-infectious diarrhea lasting more than 48 hours despite optimal loperamide treatment, manage with second-line anti-diarrheal agents, including, but not limited to Lomotil®, codeine, or octreotide, or as per institutional guidelines.
 
Interrupt ipatasertib. Rucaparib may be continued at the investigator's discretion. If diarrhea persists for >3 days following interruption of ipatasertib, rucaparib should also be interrupted. Ipatasertib and rucaparib can be resumed at the same dose or one dose lower per investigator evaluation upon improvement to Grade 1 or better.
 
Reduce ipatasertib and rucaparib by one additional dose level (see Table 3) for recurrent Grade 2 diarrhea.

Grade 3	
Rule out infectious etiology.
 
Treatment per Grade 2 management guidelines and supportive care.
 
Interrupt ipatasertib and rucaparib until diarrhea improves to Grade 1 or better.
 
Ipatasertib and rucaparib should be reduced by one dose level (see Table 3 and Table 4 ) when treatment is restarted.
 
For recurrent Grade 3 diarrhea, reduce ipatasertib and rucaparib dose by one additional dose level (see Table 3), or permanently discontinue ipatasertib and rucaparib per investigator discretion.

Grade 4	
Management as per Grade 3 guidelines. Permanently discontinue ipatasertib and rucaparib.

If both study drugs are interrupted, step-wise reintroduction of one agent at a time (e.g., ipatasertib monotherapy for several days followed by reintroduction of rucaparib if diarrhea remains Grade ≤ 1) may be pursued.

#### 5.1.4.4 Fasting Hyperglycemia

Hyperglycemia has been associated with ipatasertib and other agents targeting the *PI3K/AKT/mTOR* pathway but not associated with rucaparib or other PARP inhibitors. For this reason, management guidelines will address ipatasertib, only.

Fasting is defined as abstaining from food and drink (with the exception of water) for at least 8 hours.

Dose modification guidelines for fasting hyperglycemia attributable to study treatment are outlined in [Table 6](#) and are intended to provide guidance for fasting glucose measurements assessed in the clinic. This table is not meant to inform grading of adverse events, which should be conducted per NCI CTCAE v5.0. Decisions regarding study treatment should be made on fasting levels drawn in the clinic whenever possible.

Home glucose measurements may be used to trigger contact between patient and the investigative site team and may lead to an unscheduled clinic visit to assess fasting glucose. Guidance for when to call the investigator/site staff (or designated endocrinologist, if applicable) should be provided to patients for hypoglycemia (e.g., glucose value under 70 mg/dL) and hyperglycemia (e.g., glucose value over 300 mg/dL). Alternative thresholds may be selected as clinically indicated per investigator discretion or institutional guidance and noted in the source documents. For any patients performing home glucose monitoring, a blood glucose log should be reviewed at each clinic visit (and source data retained); entry of results into the patient's eCRF will be limited to values which result in intervention.

In the event of ipatasertib interruption, anti-diabetic medications may need to be held or reduced (per investigator judgment) and glucose should be monitored closely to minimize the risk of hypoglycemia.

**Table 6 Fasting Hyperglycemia Management Guidelines**

Severity of Fasting Hyperglycemia	Management Guideline
Fasting glucose value >ULN to 160 mg/dL (8.9 mmol/L)	
 
• Monitor fasting glucose per protocol.
 
• Consider home glucose monitoring.
 

Fasting glucose value > 160 to 250 mg/dL (>8.9–13.9 mmol/L)	
 
• Interrupt ipatasertib until the fasting glucose value decreases to ≤160 mg/dL.
 
• Initiate home glucose monitoring.
 
• Start oral anti-diabetic medications (e.g., metformin).
 
• If the patient is already on an oral anti-diabetic medication, the dose of ipatasertib should be reduced by one dose level (refer to Table 3).
 
• If the patient previously has not been receiving any oral anti-diabetic medication, ipatasertib may be resumed at the previous dose level with initiation of oral anti-diabetic medication.
 

Fasting glucose value 250 to 500 mg/dL (>13.9–27.8 mmol/L)	
 
• Interrupt ipatasertib until fasting glucose value decreases to ≤160 mg/dL.
 
• Initiate home glucose monitoring.
 
• Treat hyperglycemia as per standard of care.
 
• Start (or increase dose of) oral anti-diabetic medications (e.g., metformin).
 
• If the patient is already on an oral anti-diabetic medication, ipatasertib should be reduced by one dose level when treatment is restarted.
 
• If previously the patient has not been receiving any oral anti-diabetic medication, ipatasertib may be resumed at the previous dose level with initiation of oral anti-diabetic medication.
 
• If fasting glucose value between 250 and 500 mg/dL recurs, the dose of ipatasertib should be reduced by one dose level when treatment is restarted.
 

Severity of Fasting Hyperglycemia	Management Guideline
Fasting glucose value > 500 mg/dL (>27.8 mmol/L)	
 
• Interrupt until fasting glucose value decreases to ≤160 mg/dL.
 
• Treat hyperglycemia per standard of care.
 
• Initiate home glucose monitoring.
 
• Start (or increase dose of) oral anti-diabetic medications (e.g., metformin).
 
• Assess for volume depletion and appropriate intravenous or oral hydration.
 
• Reduced ipatasertib by one dose level when treatment is restarted.
 
• If fasting glucose value >500 mg/dL recurs, permanently discontinue ipatasertib.
 

ULN= upper limit of normal.

Note: For all grades, the patient should receive education on a diabetic diet.

#### 5.1.4.5 Nausea and/or Vomiting

Nausea and/or vomiting has been associated with both ipatasertib and rucaparib administration.

Dose reductions for nausea and/or vomiting should occur only if the symptoms persist despite a minimum of two treatments with adequate (combination) anti-emetic treatment(s), including ondansetron (or equivalent anti-emetic *treatment*; see [Table 7](#)).

For persistent nausea and/or vomiting attributable to ipatasertib, dosage-modification guidelines are outlined in [Table 7](#).

**Table 7 Nausea and Vomiting Management Guidelines**

Severity of Nausea and Vomiting	Management Guideline
Grade 1	
 
• Provide maximum supportive care as needed.
 

Grade 2	
 
• Provide maximum supportive care as needed.
 
• Provide ondansetron (or equivalent anti-emetic medication) as needed.
 

Grade $\geq 3$	
 
• Interrupt ipatasertib and rucaparib until nausea or vomiting resolves to Grade <math>\leq 2</math>.
 
• Provide maximum supportive care as needed.
 
• Provide ondansetron (or equivalent anti-emetic) as needed.
 
• If Grade <math>\geq 3</math> nausea or vomiting recurs, ipatasertib and rucaparib should be reduced by one dose level (refer to Table 3) when treatment is restarted.
 

If both study drugs are interrupted, step-wise reintroduction of one agent at a time (e.g., ipatasertib monotherapy for several days followed by reintroduction of rucaparib if nausea/vomiting remains Grade  $\leq 2$ ) may be pursued.

#### **5.1.4.6 Rash**

Rash has been associated with ipatasertib administration *and skin photosensitivity has been associated with rucaparib treatment*.

Ipatasertib should be permanently discontinued for rash associated with erythema multiforme, Stevens-Johnson syndrome, toxic epidermal necrolysis, or other suspected severe hypersensitivity or allergic reaction. Dosage modification and symptom management guidelines for skin toxicity attributable to study treatment are shown below (see [Table 8](#)). *With respect to skin photosensitivity being related to rucaparib, patients should always protect themselves appropriately when exposed to the sun.*

**Table 8 Rash Management Guidelines**

Severity of Rash	Management Guideline
Grade 1	
 
• Continue study drugs.
 
• Consider topical corticosteroids.
 

Grade 2	
 
• Interrupt ipatasertib and rucaparib treatment until resolution to Grade 1 or better or the toxicity is no longer clinically significant.
 
• Treat rash with topical corticosteroids.
 
• Consider treatment of rash with oral corticosteroids
 
• Follow above guidance and reduce ipatasertib by one dose level for recurrent Grade 2 rash.
 

Grade 3	
 
• Interrupt ipatasertib and rucaparib treatment until resolution to Grade 1 or better or the toxicity is no longer clinically significant.
 
• Treat rash with topical and systemic corticosteroids.
 
• Consider dermatological consultation.
 
• If the skin toxicity resolves to Grade 1 or better or is no longer clinically significant within 28 days, following completion of the steroid taper, ipatasertib and rucaparib may be resumed at one dose level below the previous dose (refer to Table 3).
 
• If recovery of the skin toxicity to Grade 1 or better does not occur or skin toxicity remains clinically significant continuously for 4 weeks, or Grade 3 rash recurs, permanently discontinue ipatasertib and rucaparib.
 

Grade 4	
 
• Administration of systemic steroids (oral or intravenous) is recommended. Consider dermatological consultation and skin biopsy. Ipatasertib and rucaparib should be permanently discontinued.
 

If both study drugs are interrupted, step-wise reintroduction of one agent at a time (e.g., ipatasertib monotherapy for several days followed by reintroduction of rucaparib if rash remains Grade  $\leq 1$ ) may be pursued.

#### 5.1.4.7 Pneumonitis

Pneumonitis is not known to be causally related to any of the study drugs; however, it has been observed with other drugs treating pathways similar to ipatasertib.

As pneumonitis has not been observed with rucaparib, the management guidance will address ipatasertib, only. Every effort should be made to determine the etiology of dyspnea and changes in pulmonary function (see [Table 9](#)).

**Table 9 Pneumonitis Management Guidelines**

Severity of Pneumonitis	Management Guideline
Grade 1	
 
Continue study drugs.
 
Perform CT scan and pulmonary function tests. Repeat CT scan every 8 weeks until a return to baseline.
 

Grade 2	
 
Prescribe corticosteroids if there are clinical symptoms and infectious etiology is ruled out. Interrupt ipatasertib treatment as long as corticosteroids are being given.
 
Perform CT scan and PFTs. Repeat CT scan every 4 weeks until a return to baseline.
 
If pneumonitis resolves to Grade 1 or better after completion of the steroid taper, ipatasertib may be resumed at either the previous dose or one dose level below the previous dose (see Table 3) per investigator assessment.
 
For recurrent Grade 2 pneumonitis, ipatasertib must be resumed at one dose level below the previous dose.
 
Discontinue ipatasertib if recovery to Grade 1 or better is not evident within 28 days.
 

Grade 3	
 
If infectious etiology is ruled out, prescribe corticosteroids as clinically indicated.
 
Interrupt ipatasertib treatment as long as corticosteroids are being given.
 
Perform CT scan and PFTs. Repeat CT scan every 4 weeks until a return to baseline. Bronchoscopy is recommended.
 
If pneumonitis resolves to Grade 1 or better, following completion of the steroid taper, continue ipatasertib at one dose level below the previous dose (see Table 3). Discontinue ipatasertib if recovery to Grade 1 or better is not evident within 28 days.
 
For recurrent non-infectious Grade 3 pneumonitis events, ipatasertib should be permanently discontinued
 

Grade 4	
 
If infectious etiology is ruled out, prescribe corticosteroids as clinically indicated.
 
Permanently discontinue ipatasertib.
 
Perform CT scan and PFTs. Repeat CT scan every 4 weeks until a return to baseline. Bronchoscopy is recommended.
 

CT=computed tomography; PFT=pulmonary function test.

#### 5.1.4.8 Hepatotoxicity

Liver enzyme elevations have been associated with both ipatasertib and rucaparib administration.

Permanently discontinue rucaparib and ipatasertib for any patients who develop a concurrent elevation of ALT and/or AST greater than 3× baseline and total bilirubin greater than 2× ULN and/or clinical jaundice in the absence of biliary obstruction or other

causes responsible for the concurrent elevation, including patients having abnormal liver function tests that meet Hy's law criteria (see Section 5.3.5.6).

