### **3.1.2 Definition of Dose-Limiting Toxicity**

A DLT will be defined as any of the following adverse events related to study treatments occurring during the DLT reporting period, which corresponds to the first cycle of study treatment (i.e., from Cycle 1, Day –7 to Day 28; Cycle 1 has 35 days):

- Any death related to study treatment
- Grade 4 neutropenia lasting for  $\geq 7$  days
- Grade  $\geq 3$  neutropenia complicated by fever  $\geq 38^{\circ}\text{C}$  or infection
- Grade 4 thrombocytopenia lasting for  $\geq 7$  days
- Grade  $\geq 3$  thrombocytopenia complicated by hemorrhage or that requires transfusion
- Study treatment-related Grade  $\geq 3$  non-hematologic toxicity (graded according to the NCI CTCAE, v5.0) except for the following:
  - Grade 3 fatigue, asthenia, fever, anorexia, or constipation
  - Grade 3 nausea, vomiting, or diarrhea that responds to maximal supportive care within 72 hours
  - Grade 3 rash that resolves to Grade 1 within 7 days with maximal supportive care
  - Grade 3 hyperglycemia that is controlled with subcutaneous insulin
  - *Grade 3 ALT or AST elevation that is not accompanied by a concurrent increase in bilirubin (i.e., greater than the upper limit of normal [ULN])*
  - *Any other Grade 3 laboratory abnormality that is asymptomatic and is deemed not to be clinically significant by the investigator*

Patients who miss seven or more doses of either ipatasertib or rucaparib during the DLT-evaluation period for reasons other than a DLT will be replaced. In addition, patients who are discontinued from the study prior to completing the DLT-evaluation period for reasons other than a DLT (e.g., disease progression, consent withdrawn) will also be replaced. If a patient experiences a DLT, study treatment will be interrupted immediately for that individual and a safety assessment will be conducted.

The NCI CTCAE v5.0 will be used to characterize the toxicity profile of the study treatments for all patients.

An interim analysis for safety (including DLTs) will be performed by the Sponsor prior to the Dose-Expansion Phase (Part 2) to assess data from all patients in the Dose-Escalation Phase (Part 1). The interim analysis will be completed after the last evaluable patient in Part 1 has completed the first cycle of treatment. The combination dose levels demonstrating acceptable safety will be carried forward to the Dose-Expansion Phase (Part 2) of the study.

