**Table 10 Hepatotoxicity Management Guidelines**

Severity of LFT Elevation	Management Guideline

Grade 1 AST or ALT  <math>>ULN-3.0 \times ULN</math> if baseline was normal; <math>1.5-3.0 \times</math> baseline if baseline was abnormal or total bilirubin <math>>ULN-1.5 \times ULN</math> if baseline was normal; <math>>1.0-1.5 \times</math> baseline if baseline was abnormal
	
 
• Continue study drugs.
 
• Monitor LFTs until values resolve to baseline values.
 

Grade 2 AST or ALT  <math>>3.0-5.0 \times ULN</math> if baseline was normal; <math>>3.0-5.0 \times</math> baseline if baseline was abnormal or total bilirubin <math>>1.5-3.0 \times ULN</math> if baseline was normal; <math>>1.5-3.0 \times</math> baseline if baseline was abnormal
	
 
• Continue study drugs.
 
• The frequency of liver function test monitoring should be increased as clinically indicated if the investigator judges that the laboratory abnormalities are potentially related to study medication.
 

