
Grade 3 AST or ALT  <math>>5.0-20.0 \times ULN</math> if baseline was normal; <math>>5.0-20.0 \times</math> baseline if baseline was abnormal or total bilirubin <math>>3.0-10.0 \times ULN</math> if baseline was normal; <math>>3.0-10.0 \times</math> baseline if baseline was abnormal
	
 
• Interrupt ipatasertib until improvement of AST/ALT to Grade <math>\leq 2</math>. Treatment may be resumed at previous dose level.
 
• Continuation of rucaparib with elevation of AST/ALT up to Grade 3 is permitted provided bilirubin is <math>< ULN</math> and alkaline phosphatase is <math>< 3 \times ULN</math>. If levels do not decline within 2 weeks or they continue to rise, treatment interruption and improvement to Grade <math>\leq 2</math> will be required before rucaparib can be resumed with reduction by one dose level.
 
• Consider hepatology consult.
 
• Following treatment resumption, monitor serum transaminases and bilirubin at a minimum every 2 weeks for 3 months and monthly thereafter.
 
• If another Grade 3 event occurs, interrupt rucaparib and ipatasertib. On return of LFTs to Grade <math>\leq 2</math>, resume ipatasertib, reducing the dose by one level and rucaparib, reducing the dose by one level.
 
• Further Grade 3 occurrences must result in permanent discontinuation of rucaparib and ipatasertib.
 

Grade 4 AST or ALT <math>>20.0 \times ULN</math> if baseline was normal; <math>>20.0 \times</math> baseline if baseline was abnormal or total bilirubin <math>>10.0 \times ULN</math> if baseline was normal; <math>>10.0 \times</math> baseline if baseline was abnormal
	
 
• Permanently discontinue treatment with ipatasertib and rucaparib.
 

LFT=liver function test; QD=once daily; ULN=upper limit of normal.

If both study drugs are interrupted, step-wise reintroduction of one agent at a time (e.g., ipatasertib monotherapy for several days followed by reintroduction of rucaparib if liver enzymes remain Grade  $\leq 2$ ) may be pursued.

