#### **5.1.4.9 Dose Modifications**

##### **Rucaparib Dose Modifications**

Potential dose reduction steps for rucaparib based on different current doses of rucaparib are shown in [Table 11](#). In Part 1, during the DLT evaluation period (Cycle 1), dose reductions of rucaparib are not allowed for reasons other than a DLT or a decision by the Sponsor based on emerging safety data.

In Part 1, during the DLT evaluation period (Cycle 1), dose interruptions of rucaparib are not allowed for reasons other than toxicity. Patients are eligible for safety and DLT evaluation of the dose cohort if they receive at least 70% of the planned total dose of each study drug within Cycle 1 or they experience a DLT at any time during Cycle 1. During the remainder of the study, treatment with rucaparib may be interrupted for up to 28 days (1 cycle) for toxicity or reasons unrelated to toxicity. If rucaparib is withheld because of adverse events for >28 days, the patient will be discontinued from rucaparib. If, however, in the judgment of the investigator, the patient is likely to derive clinical benefit from rucaparib after a hold of >28 days, study drug may be restarted with the approval of the Medical Monitor.

Once a RP2D has been established at the end of Part 1, those patients in Part 1 who are treated at a dose below the RP2D and are tolerating study drugs may be escalated to the RP2D at the discretion of the investigator with approval from the Medical Monitor.

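### A related Cycle 1 liver event that permanently ends both drugs under Section 5.1.4.8 can have both liver values below Grade 3, and on those values it is missing from the DLT count behind the one-third RP2D rule

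*Combined protocol and SAP*

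**What the plan says.** **Stop rule (5.1.4.8).** "Permanently discontinue rucaparib and ipatasertib for any patients who develop a concurrent elevation of ALT and/or AST" above 3 × baseline with total bilirubin above 2 × ULN and/or clinical jaundice, when biliary obstruction and other causes are absent. No minimum CTCAE grade is attached. Section 5.3.5.6 describes essentially this pattern as an indicator of severe liver injury, and 5.2.3 makes it an event of special interest.

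**Grades (Table 10).** The row "Grade 2 AST or ALT" covers transaminases above 3 and up to 5 × ULN and bilirubin above 1.5 and up to 3 × ULN when baselines are normal. If a baseline is abnormal, the same multiples apply to that baseline.

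**DLT definition (3.1.2).** Apart from death, the route for a liver event is related Grade 3 or higher "non-hematologic toxicity (graded according to the NCI CTCAE, v5.0) except for the following" and then a list of exceptions. The one liver-specific item is an exception: "Grade 3 ALT or AST elevation that is not accompanied by a concurrent increase in bilirubin". It removes events and adds none. Neither Hy's Law nor permanent discontinuation is listed as a DLT.

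**Who counts.** Section 3.1.2: "Patients who miss seven or more doses of either ipatasertib or rucaparib" in the DLT period for non-DLT reasons are replaced, and so are patients discontinued from the study before the period ends for such reasons. Section 5.1.4.9 counts a patient as evaluable who received at least 70% of the planned dose of each drug "or they experience a DLT at any time during Cycle 1".

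**RP2D rule (3.1.1.1).** An acceptable safety profile, at least 6 patients, and DLTs in fewer than one-third of them.

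**The concern.** The protocol treats this event as serious enough to end the combination for that patient in Cycle 1, yet the only numeric limit in the RP2D rule can fail to register it. The ordering is also inverted: a milder pattern, after which Table 10 provides for resuming treatment, is a DLT, while the pattern that stops both drugs for good is not.

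At stake is a single cohort of six. If the uncounted case falls beside one listed DLT, it decides whether the dose level passes or fails. Whether it is counted depends on how an investigator names and grades it, and about 20 sites take part (9.4).

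**Working it through.** **1. The plan's own figure.** Four dose levels × about 6 patients = 24, as stated in 6.1. With six patients, 1/6 = 16.7% passes and 2/6 = 33.3% does not, because it is not below one-third.

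**2. Overlap of stop rule and grades (Table 10).**
- ALT baseline at ULN, bilirubin baseline normal: ALT above 3 and up to 5 × ULN with bilirubin above 2 and up to 3 × ULN meets the stop rule with both values at Grade 2. Example: ALT 4 × ULN, bilirubin 2.5 × ULN.
- ALT baseline 0.5 × ULN: the ALT limb is met above 3 × 0.5 = 1.5 × ULN, which is Grade 1.
- ALT baseline 1.5 × ULN (allowed at entry): ALT stays below Grade 3 up to 5 × 1.5 = 7.5 × ULN.

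**3. The inversion (normal baselines, related events).**
- ALT 5.1 × ULN with a concurrent rise in bilirubin to 1.1 × ULN: Grade 3, and the ALT/AST exception fails because bilirubin exceeds ULN. The last exception covers only other laboratory abnormalities. This is a DLT, yet for Grade 3 Table 10 says of ipatasertib "Treatment may be resumed at previous dose level" and lets rucaparib return one level lower.
- ALT 4.9 × ULN with bilirubin 2.9 × ULN: both Grade 2. Both drugs end permanently, and the values are not a DLT.

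**4. What happens to the patient, by stop day.** Rucaparib starts on the evening of Day 1 (4.3.2.2), so Cycle 1 has 1 + 27 × 2 = 55 planned doses. Ipatasertib has 7 + 28 = 35. A stop before dosing on Day d leaves 2d − 3 rucaparib and d + 6 ipatasertib doses received.

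| Stop day | Rucaparib received | Rucaparib missed | 70% rule | Seven-missed rule |
|---|---|---|---|---|
| 8 | 13/55 = 23.6% | 42 | not evaluable | replace |
| 15 | 27/55 = 49.1% | 28 | not evaluable | replace |
| 20 | 37/55 = 67.3% | 18 | not evaluable | replace |
| 21 | 39/55 = 70.9% | 16 | evaluable | replace |
| 25 | 47/55 = 85.5% | 8 | evaluable | replace |
| 26 | 49/55 = 89.1% | 6 | evaluable | not triggered |

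Ipatasertib does not alter this: Day 21 gives 27/35 = 77.1%, and Day 26 gives 32/35 = 91.4% with 3 missed.

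- Up to Day 20, which includes the Day 8 and Day 15 panels with their 2-day windows, both dose rules exclude the patient, who is replaced.
- On Days 21 to 25 the two dose rules conflict.
- From Day 26 neither dose rule removes the patient. Whether the patient stays as a non-DLT or is replaced depends on whether discontinuation from the study, in 3.1.2, includes permanent treatment discontinuation. Late detection is possible: the Cycle 2 Day 1 panel may be drawn up to 96 hours before dosing (Appendix 1, footnote q), so from Day 25.

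In every branch the event is absent from the numerator.

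**5. One cohort.** One such case and one listed DLT among the other five: counted, 2/6 fails. As written, it reads 1/6 if the patient is kept, or 1/6 after replacement if the replacement has no DLT.

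**6. How often, under assumed rates.** Let c be the rate of listed DLTs and q the rate of uncounted stop events. They are taken as mutually exclusive within a patient, with patients independent. Chance of passing = (1 − p)^6 + 6p(1 − p)^5, with p = c + q if counted, c/(1 − q) if replaced, and c if kept. With c = 30%:

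| q | Counted | Replaced | Kept |
|---|---|---|---|
| 1% | 39.9% | 41.4% | 42.0% |
| 2% | 37.8% | 40.7% | 42.0% |
| 5% | 31.9% | 38.7% | 42.0% |

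The pattern in step 5 has probability 6q × 5c × (1 − c − q)^4. At q = 2%:
- c = 30%: 0.12 × 1.5 × 0.68^4 = 3.8%. This is the share of cohorts whose result changes if the patient is kept. If the patient is replaced, multiply by the chance that the replacement has no listed DLT, 1 − 0.30/0.98 = 0.694, which gives 2.7%.
- c = 15%: 0.12 × 0.75 × 0.83^4 = 4.3% if kept; × 0.847 = 3.6% if replaced.

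**The case against.** **The decision has other safeguards.** The RP2D also needs an acceptable safety profile, the event is reported within 24 hours, the Sponsor reviews all Part 1 patients before expansion, and Part 2 evaluates the dose further. This stands. A reader might infer that a dose with such a case would pass unseen; the documents do not support that. What remains is that discretion replaces the numeric limit for this event.

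**Recording rules put the diagnosis first.** Sections 5.3.5.1 and 5.3.5.6 prefer a diagnosis to laboratory values. Table 14 would allow Grade 3 for a medically significant event not listed in CTCAE, and 5.3.5.3 records the worst severity reached. This narrows the gap to cases that peak below Grade 3 and are not graded 3 as a diagnosis. No text requires Grade 3 for them. Nor may one infer that all Hy's Law cases escape: if either value reaches Grade 3 in the DLT period, the related event already counts.

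**The third replacement clause.** It would be tempting to say that from Day 26 the patient simply stays as a non-DLT. Section 3.1.2 gives disease progression as an example of leaving the study, and 4.6.1 applies the same replacement exception to patients who stop treatment, so replacement is a fair reading. The text settles neither, and neither puts the event in the numerator.

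**A deliberate design choice.** No rule says a permanent stop must be a DLT, and the amendment that clarified the ALT/AST item left the Grade 3 threshold in place. That is fair, but nothing in the protocol explains why the pattern it calls an indicator of severe liver injury should fall outside the count.

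**Conclusion.** The gap is real on the text: a related event in the DLT period can meet 5.1.4.8 with both liver values at Grade 2 or lower and, on those values, is not a DLT under 3.1.2. The stop day determines whether the patient is replaced, disputed or possibly kept; it never brings the event into the count.

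The average effect is small. With assumed rates of 2% uncounted and 30% listed, omission raises the chance of passing by 40.7 − 37.8 = 2.9 points (replaced) or 42.0 − 37.8 = 4.2 points (kept). The single-case pattern changes the result in about 2.7% to 3.8% of cohorts. These figures rest wholly on assumed rates and should not be read as a material inflation of the rule's error. The point is the individual cohort, where one such case beside one listed DLT separates pass from fail. This is a cheap improvement that should be made, not a defect that invalidates the escalation.

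**What to change.** Add one bullet to the DLT list in 3.1.2: *any treatment-related event in the DLT period that meets the permanent-discontinuation criteria of Section 5.1.4.8, whatever its CTCAE grade; the Grade 3 exceptions do not apply to it.*

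The event then counts in numerator and denominator on any stop day, because 5.1.4.9 treats a patient with a DLT as evaluable at any dose received and 3.1.2 replaces patients only for non-DLT reasons. For these patients the Day 21 to 25 conflict and the Day 26 ambiguity both disappear.

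The cost is one line, with no new data or visits. The downside is that a cohort may fail on a case with a low baseline ALT (from 0.5 × ULN, the ALT limb is met above 1.5 × ULN), although 5.1.4.8 already ends both drugs for that patient. Attribution remains an investigator judgment, for example in Gilbert's syndrome, where entry bilirubin may be up to 3 × ULN.
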